4.3 Justification for Dose

To date, 4 Phase 1 clinical studies have been completed in which a total of 36 HVs have been exposed to AZD4831 at doses 5 to 405 mg as single doses and 53 HVs at doses 2.5 to 45 mg as multiple doses. In the HV, AZD4831 was generally well tolerated with the exception of generalised maculopapular rash seen around 7-10 days after the first dose: in the single ascending dose study (D6580C00001), 1 HV out of 6 receiving 45 mg, 1 HV out of 6 receiving 135 mg and 2 HVs out of 6 receiving 405 mg; in the MAD study (D6580C00004), 2 HVs out of 8 receiving 15 mg and 2 HVs out of 5 receiving 45 mg.

In a single-blind MAD study in Japanese and Chinese HVs (Study D6580C00008), maculopapular rash was reported in 5 of 24 Japanese and Chinese HVs who received AZD4831. Maculopapular rash CTCAE Grade 1 was reported in one of 6 Japanese HVs on 5 mg AZD4831 and maculopapular rash Grade 2 was reported in one of 6 Chinese participants on 5 mg AZD4831 and in 3 of 6 Japanese HVs on 10 mg AZD4831.

A Phase 2a study intended to assess target engagement, safety, and tolerability of AZD4831 in participants with HFpEF was prematurely terminated during the COVID-19 pandemic after meeting pre-defined target engagement, safety, and tolerability criteria (Study D6580C00003). One participant out of 27 receiving 5 mg AZD4831 was discontinued from study treatment due to Grade 3 generalised maculopapular rash.

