The dose selection for Part A is based on target engagement (MPO inhibition) data from the Phase 1 MAD study (HV), the Phase 2a study (HFpEF), and data from the MAD study in Japanese and Chinese healthy participants. Two dose levels are being proposed (2.5 and 5 mg) based on expected efficacy (lower dose) and safety (upper dose). The 2.5 mg dose is predicted to be the lowest clinically relevant dose (predicted to result in approximately 50% MPO inhibition) and 5 mg is the upper safety dose since no rash was observed at doses below 15 mg AZD4831 in the Phase 1 MAD study (HV), in 1 of 27 participants at 5 mg AZD4831 in the Phase 2a study (HFpEF), and in 2 of 12 HVs on 5 mg AZD4831 in the Japanese and Chinese MAD study. The dose selection for Part B will be based on totality of data in Part A, ie, safety and effect on symptoms and functions as well as effects on other biomarkers/efficacy endpoints, in order to select the dose with the predicted optimal risk/benefit ratio. The dose selection for Part B will be done by a firewalled URC (to maintain blinding) at an interim

analysis conducted when it is assessed there is a sufficient number of participants randomised and data accrued.

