7 DISCONTINUATION OF STUDY INTERVENTION AND PARTICIPANT DISCONTINUATION/WITHDRAWAL

7.1 Discontinuation of Study Intervention

It may be necessary for a participant to permanently discontinue (definitive discontinuation) study intervention. If study intervention is permanently discontinued, the participant should remain in the study, ie, continue to participate in scheduled study visits and evaluations.

Note that discontinuation from study intervention is NOT the same thing as a withdrawal from the study. For procedures in the case of withdrawal from the study, see Section 7.2.

At each visit, participants will be instructed to contact the investigator immediately, if rash or skin reaction has developed. If maculopapular rash grade 1, 2, or 3 has developed, participant must be permanently discontinued from the study intervention and AZ medical staff should be informed.

- Grade 1: Macules/papules covering < 10% Body Surface Area with or without symptoms (eg, pruritus, burning, tightness).

- Grade 2: Macules/papules covering 10 - 30% Body Surface Area, with or without symptoms (eg, pruritus, burning, tightness); limiting Instrumental ADL (refer to preparing meals, shopping for groceries or clothes, using the telephone, managing money, etc); rash covering > 30% Body Surface Area with or without mild symptoms.
- Grade 3: Macules/papules covering > 30% Body Surface Area, with moderate or severe symptoms; limiting Self-care ADL (refer to bathing, dressing and undressing, feeding self, using the toilet, taking medications, and not bedridden).

If the participant develops a rash or skin reaction that is not considered a maculopapular rash, but is a generalised rash/skin reaction or is considered to be an SAE, the participant must be permanently discontinued from the study intervention and AZ medical staff should be informed.

For further information and skin reaction evaluation guidance, see Appendix B 5.

Study participants also may be discontinued from study intervention in the following situations:

- Participant decision. The participant is at any time free to discontinue treatment, without prejudice to further treatment.
- Adverse Event or other safety reasons as judged by the Investigator and/or sponsor where continued treatment may put the participant at undue risk.
- Development of uncontrolled and clinical significant **CCI** as judged by the Investigator.
- Severe non-compliance with the CSP.
- Pregnancy

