4.2 Endpoint Analyses

This section covers details related to the endpoint analyses such as primary, secondary, and exploratory endpoints including sensitivity and supportive analyses.

Primary estimand

The primary estimand is defined by the following attributes:

- **Endpoint:** Change from baseline in variable at analysis timepoint.
- **Treatment:** Randomised treatment group (regardless of actual received treatment), AZD4831 2.5mg/5mg or placebo, administered in addition to optimal background therapy for co-morbidities.
- **Population:** Subjects aged ≥ 40 years with an established diagnosis of HF with LVEF $> 40\%$, and at least one or more of structural heart disease, signs of increased left ventricular filling pressure, signs of significant diastolic dysfunction, or a recent hospitalisation for decompensated HF and alive. This is implemented on evaluable subjects defined by a subset of FAS (see Table 2) which have available measurements of the efficacy endpoints at baseline and analysis timepoint.
- **Population-level summary:** Difference in adjusted mean change from baseline to analysis timepoint or adjusted geometric mean ratio.
- **Handling of intercurrent events:** Treatment policy strategy combined with principal stratum strategy
 - Initiation or change of concomitant medication and permanent premature discontinuations of IP will be handled by a treatment policy strategy, i.e., ignoring these intercurrent events, implemented by including all available data.
 - Subjects with intercurrent events resulting in missing assessments of the primary endpoints, e.g., terminal events or withdrawal from the study, are expected to be very few and will be excluded from the analysis (principal stratum strategy).

Supplementary estimands

Supplementary analyses of the primary objectives will be conducted using four different supplementary estimands. The treatment attribute for the supplementary estimands is the same as for the primary estimand.

For the first supplementary estimand, the other attributes are the following:

- **Endpoint:** Change from baseline in variable at analysis timepoint.
- **Population:** Subjects aged ≥ 40 years with an established diagnosis of HF with LVEF $> 40\%$, and at least one or more of structural heart disease, signs of increased left ventricular filling pressure, signs of significant diastolic dysfunction, or a recent hospitalisation for decompensated HF. Implemented by FAS.

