- **Population-level summary:** Difference in adjusted mean change from baseline to analysis timepoint.
- **Handling of intercurrent events:** Treatment policy strategy combined with hypothetical strategy
 - Initiation or change of concomitant medication and permanent premature discontinuations of IP will be handled by a treatment policy strategy, i.e., ignoring these intercurrent events, implemented by including all available data.
 - Deaths will be handled by a hypothetical strategy for the hypothetical scenario where death cannot occur. Under the assumption that death is a non-informative event, this is implemented by including all available data up to time of death.

For the second supplementary estimand, the other attributes are the following:

- **Endpoint:** Change from baseline in variable at analysis timepoint with death considered worst possible outcome.
- **Population:** Subjects aged ≥ 40 years with an established diagnosis of HF with LVEF $> 40\%$, and at least one or more of structural heart disease, signs of increased left ventricular filling pressure, signs of significant diastolic dysfunction, or a recent hospitalisation for decompensated HF. Implemented by FAS.
- **Population-level summary:** Difference in adjusted median change from baseline to analysis timepoint.

- **Handling of intercurrent events:** Treatment policy strategy combined with composite variable strategy.
 - Initiation or change of concomitant medication and permanent premature discontinuations of IP will be handled by a treatment policy strategy, i.e., ignoring these intercurrent events, implemented by including all available data.
 - Death is handled by incorporating this intercurrent event in the endpoint and consider it as worst possible outcome (composite variable strategy).
 - Subjects with intercurrent events resulting in missing assessments of the primary endpoints other than death are expected to be very few and will be excluded from the analysis (principal stratum strategy).

For the third supplementary estimand, the other attributes are the following:

- **Endpoint:** Change from baseline in variable at analysis timepoint.

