- **Population:** Subjects aged ≥ 40 years with an established diagnosis of HF with LVEF $> 40\%$, and at least one or more of structural heart disease, signs of increased left ventricular filling pressure, signs of significant diastolic dysfunction, or a recent hospitalisation for decompensated HF who are alive and have not permanently prematurely discontinued IP. This is implemented on evaluable subjects defined by a subset of FAS which have not discontinued IP and have available measurements of the efficacy endpoints at baseline and analysis timepoint.
- **Population-level summary:** Difference in adjusted mean change from baseline to analysis timepoint or adjusted geometric mean ratio.
- **Handling of intercurrent events:** Treatment policy strategy combined with principal stratum strategy.
 - Initiation or change of concomitant medication will be handled by a treatment policy strategy, i.e., ignoring these intercurrent events. Implemented by including all available data.
 - Subjects with intercurrent events resulting in missing assessments of the primary endpoints, e.g., terminal events or withdrawal from the study, are expected to be very few and will be excluded from the analysis (principal stratum strategy).

- Subjects who have discontinued IP will be excluded from the analysis (principal stratum strategy).

For the fourth supplementary estimand, the other attributes are the following:

- **Endpoint:** Change from baseline in variable at analysis timepoint.
- **Population:** Subjects aged ≥ 40 years with an established diagnosis of HF with LVEF $> 40\%$, and at least one or more of structural heart disease, signs of increased left ventricular filling pressure, signs of significant diastolic dysfunction, or a recent hospitalisation for decompensated HF. This is implemented on evaluable subjects defined by a subset of FAS (see Table 2) which have available measurements of the efficacy endpoints at baseline and analysis timepoint.
- **Population-level summary:** Difference in adjusted mean change from baseline to analysis timepoint or prior to death, if earlier, as a function of baseline.
- **Handling of intercurrent events:** Treatment policy strategy combined with while-alive strategy and principal stratum strategy
 - Initiation or change of concomitant medication and permanent premature discontinuations of IP will be handled by a treatment policy strategy, i.e., ignoring these intercurrent event, implemented by including all available data.

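### SAP 4.2 labels an observed on-treatment completer subset a principal stratum in the third supplementary estimand; randomisation does not protect that comparison, and no identifying assumption is stated

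*SAP*

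**What the plan says.** SAP 4.2 defines the third supplementary estimand on subjects who are alive and have not permanently and prematurely discontinued IP. It is implemented on a "subset of FAS which have not discontinued IP and have available measurements of the efficacy endpoints at baseline and analysis timepoint". Under intercurrent events it adds: "Subjects who have discontinued IP will be excluded from the analysis (principal stratum strategy"). Table 2 lists ANCOVA as the analysis for KCCQ-TSS and 6MWD at 16 weeks. The same estimand is reused for NT-proBNP (4.2.5.5), LV-GLS, LAVI and LVMI (4.2.6.5) and IL-6 (4.2.8.5).

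The primary estimand in the same section treats this event differently: "permanent premature discontinuations of IP will be handled by a treatment policy strategy".

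Protocol 7.1 sets a mandatory stop: "If maculopapular rash grade 1, 2, or 3 has developed, participant must be permanently discontinued from the study intervention". It also intends follow-up to continue: "If study intervention is permanently discontinued, the participant should remain in the study, ie, continue to participate in scheduled study visits and evaluations". Week-16 values are therefore meant to exist for the subjects whom this estimand removes.

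**The concern.** Membership of a principal stratum is fixed by potential behaviour under both arms, so it cannot be affected by the treatment received. Observed discontinuation can be. Maculopapular rash is listed in Protocol Table 3 as an identified risk of AZD4831, and any grade ends dosing. Removing people by observed discontinuation conditions on a post-randomisation event that the drug may cause. The remaining active and placebo subjects then need not be the same kind of patient.

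What is at stake is what the result can be said to show. Under the present label, a reader could take it as the causal effect in people who would stay on IP under either treatment. The stated analysis does not estimate that without further assumptions, and SAP 4.2 gives none for this estimand. The SAP is more careful elsewhere. It states a non-informative assumption for death in the first supplementary estimand and for on-treatment censoring in the safety estimand (4.6). It also justifies excluding subjects with missing assessments by expecting very few of them. The IP-discontinuation bullet carries neither kind of statement.

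**Working it through.** **1. Who is in each subset.** Classify subjects by what they would do on each arm.

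| Type | Active completer | Placebo completer |
|---|---|---|
| Stays on IP under both | yes | yes |
| Would stop only on active | no | yes |
| Would stop only on placebo | yes | no |
| Would stop under both | no | no |

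The principal stratum is the first row. The planned comparison is rows 1 and 3 against rows 1 and 2. The two agree in general only if rows 2 and 3 are empty or their outcomes do not differ from those in row 1. A mandatory stop for a drug-risk rash makes row 2 unlikely to be empty.

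**2. Timing.** Protocol 4.3 reports, in healthy volunteers, "generalised maculopapular rash seen around 7-10 days after the first dose". That is well before week 16.

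**3. Yardstick.** The documents attach no figure to this estimand, so I use the Part A design effect. With SD 20 (SAP section 2), 200 per arm and two-sided alpha 0.05:
- Critical value = 1.96 × 20 × √(2/200) = 3.92, against the stated 3.9.
- Power at 6.0 points = 85.1%, against the stated 85%.

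The protocol's SD of 18 does not reproduce these figures (critical value 3.53).

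**4. Size of the shift.** Let p be the share stopping in an arm and k the amount by which stoppers do worse than non-stoppers, taken as equal in both arms. Each arm's overall mean is its completer mean minus p × k. The completer contrast therefore exceeds the all-subjects contrast by k × (p_active − p_placebo). With no drug effect, all of that is bias.

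The inputs are assumptions: k = 5-10 KCCQ-TSS points, active 10-15%, placebo 5-7%.
- Smallest: 5 × (0.10 − 0.07) = 0.15 points; 0.15/6 = 2.5%.
- Largest: 10 × (0.15 − 0.05) = 1.0 point; 1.0/6 = 17%.
- k = 0 gives no shift, and a negative k reverses the sign.

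**5. Cross-check on the 5 mg rash counts in Protocol 4.3.** Rash was seen "in 1 of 27 participants at 5 mg AZD4831 in the Phase 2a study (HFpEF") and in 2 of 12 Japanese and Chinese healthy volunteers. Assume no rash stops on placebo and k = 10.

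| Rate | Expected of 220 on 5 mg | Shift (points) |
|---|---|---|
| 1/27 = 3.7% | 8 | 0.037 × 10 = 0.37 |
| 3/39 = 7.7% (both studies) | 17 | 0.077 × 10 = 0.77 |
| 2/12 = 16.7% | 37 | 0.167 × 10 = 1.67 |

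Exact 95% intervals are 0.1-19.0% for 1/27 and 2.1-48.4% for 2/12, so these rates are only loosely known. For pooled doses, the shift is about half if rash is confined to 5 mg. A simulation of the 5 mg contrast (10,000 runs per setting) gave shifts of 0.37, 0.79 and 1.66.

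**6. What on-drug data an early stopper has.** Protocol Table 1 and SAP 4.2.3.4 place the first scheduled on-site post-baseline KCCQ at week 12. In the visible parts of Protocol Figure 1, the first post-baseline 6MWT, echocardiogram, NT-proBNP and IL-6 are at week 16. Someone who stops at day 7-10 has no on-drug value of any of these endpoints after baseline.

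**The case against.** - **No decision rests on this analysis.** This stands. The primary, first, second and fourth estimands all use treatment policy for IP discontinuation, and the third is outside the testing sequence in SAP 3.3.4. A reader might infer that the trial's type I error is at risk; it is not.
- **Stopping mainly on active drug is not documented.** This stands. A reader might infer it from the rash rule, but the documents give no placebo rash rate and no stopping rates by arm for any reason. Rash is only one reason for stopping.
- **Nothing links rash to KCCQ-TSS or 6MWD.** This also stands. The documents do not support reading the bias as favouring AZD4831. The only rate in the target disease is 1/27, and the larger shift in step 5 needs the rate from 12 healthy volunteers.
- **The arithmetic may not be all bias.** If active stoppers do worse because they lost a drug effect, part of the gap belongs to the on-drug contrast. The formula is pure bias only when there is no drug effect.
- **An MMRM would not cure it.** This is largely right. Early stoppers contribute no on-drug outcome, so an MMRM rests on nearly the same completers. A reader might also think that the first supplementary estimand already supplies the handling, because it is titled "Treatment policy strategy combined with hypothetical strategy". In it, only death is hypothetical; IP discontinuation is treatment policy.
- **The detail may be elsewhere.** The body of SAP 4.2.1.6 was not in the text available to me, so an assumption stated there cannot be excluded. It would not make the subset defined in 4.2 a principal stratum.

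These points limit the size of the concern and shape the repair. None of them rescues the label.

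**Conclusion.** The concern holds as one of definition and interpretation. The third supplementary estimand is named a principal stratum but implemented as an observed completer subset, and stopping can be caused by the drug. The stated ANCOVA does not estimate the stated target without assumptions that SAP 4.2 does not give.

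The direction and size of any bias are unknown. The range of 0.15-1.0 KCCQ-TSS points rests wholly on the assumed stopping rates and outcome gap. It shows the scale and does not predict the bias. The consequence is confined to what this supplementary analysis, and its reuse for the secondary endpoints, can be said to show.

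A second gap is that SAP 4.2 does not say whether discontinuation means before the analysis timepoint or at any time. Read literally, someone who stops at week 30 would be dropped from the week-16 analysis despite being on drug at week 16.

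**What to change.** In SAP 4.2 and Table 2, for the third supplementary estimand and wherever it is reused:

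1. Remove the principal-stratum label for IP discontinuation and define the handling as a hypothetical (on-treatment) strategy.
2. Set to missing only values recorded after IP stop, so that subjects who stop after the analysis timepoint keep their on-drug value.
3. State the missing-at-random assumption. Say that for early stoppers, who have no on-drug post-baseline value, it rests on baseline covariates alone, and that an MMRM therefore adds little protection.
4. Tabulate excluded subjects by arm and reason, beside the Kaplan-Meier plot of IP discontinuation already planned in SAP 4.6.1.2.

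The cost is SAP wording, a changed data rule and modest programming. For subjects who stop before week 16, the estimate will change little; what changes is the claim made for it. The result will still depend on an assumption that the data cannot test.

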8.6.4 Collection of Mandatory Samples for Potential Diagnostic Assay Development

Plasma and serum samples for potential diagnostic development are required and will be collected from all participants in Part A and B of this study as specified in the SoA (See Section 1.3). The intention of these samples is to provide additional samples for assessment of the variability in levels of candidate biomarkers that show potential to predict response to treatment with AZD4831 and to bridge from a Research Use Only assay to a diagnostic assay. The samples may be used for commercial diagnostic assay development.

Plasma and serum samples will be collected, handled, labelled, stored, and shipped as detailed in the Laboratory Manual. For storage, re-use and destruction of samples, see Section 8.5 and Appendix C.

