- For KCCQ-TSS, due to the assumed treatment-by-baseline interaction, the power was assessed through simulation of normally distributed values truncated to the range [0, 100]. Simulated studies are analysed with ANCOVA with an interaction effect between treatment group and baseline KCCQ-TSS. The global null hypothesis of no impact of treatment group on the expected change from baseline is assessed by a likelihood-ratio test comparing this model to a model with no treatment effects.

Approximately 820 participants will be randomised in 1:1 allocation, of which we estimate approximately 745 will have complete safety data. The sample size is chosen to have enough participants exposed to AZD4831 at the therapeutic dose to fulfil the minimum requirement in the ICH E1 guideline on population exposure, taken together with Part A of this study as well as a second function and symptom study with a similar design as Part B, and Phase 1 studies completed ahead of submission.

With the proposed number of participants, and under the alternative hypothesis for the treatment effect represented by the line $y = 18.2 - 0.112 * \text{BASEKCCQ-TSS}$ for the difference in expected change from baseline with AZD4831 compared to placebo as a function of the baseline score, the global null hypothesis can be rejected in more than 99% of simulations.

For 6MWD, change from baseline in 6MWD is assumed to be approximately normally distributed with a standard deviation of 70 meters. Power calculations are based on a two-sample t-test with shared variance. Assuming a true difference in mean change from baseline of 19 meters, the power to reject the null hypothesis is 95% with the proposed number of participants. The critical value is 11.

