Primary analysis of exploratory endpoints targeting primary estimand	CCI                                    [figure not shown]75 years)
- Sex (Male, Female)
- Race (Black or African American, Native Hawaiian or other Pacific Islander, American Indian or Alaska Native, Asian, White, Other)
- Hispanic/Latino (Yes/No)
- Geographic region (Europe, North America, South America, Asia and Australia) with regions defined as in Section 4.1.3.
- BMI (<30, \geq 30)
- Alcohol consumption (Never, Former, Current)
- Nicotine consumption (Never, Former, Current)
- KCCQ-TSS (points) (\leq 80, >80)
- 6MWD (meters) (\leq 350, >350)
- Hospitalized for HF prior to randomisation (Yes/No)

- NYHA functional classification (II, III, IV)
- LVEF (%) (<50, \geq 50)
- History of atrial fibrillation (Yes/No)
- History of atrial flutter (Yes/No)
- History of hypertension (Yes/No)
- NT-proBNP (\leq Median, $>$ Median)
- Neutrophil count ($\leq 4 \times 10^9/L$, $> 4 \times 10^9/L$)
- HbA1C (%) (<6.5, \geq 6.5)
- eGFR, calculated according to CKD-EPI S-Creatinine equation (mL/min/1.73m²) (\leq 60, $>$ 60)
- S-Cystatin C (\leq Median, $>$ Median)
- MPO levels (\leq Median, $>$ Median)
- Urinary albumin-to-creatinine ratio (UACR) (\leq Median, $>$ Median)
- Ceruloplasmin (\leq Median, $>$ Median)
- Iron deficiency determined by Serum Ferritin in combination with Transferrin saturation (Serum Ferritin <100ng/mL OR Serum Ferritin 100-299 ng/mL with Transferrin saturation <20%) (Yes/No)
- Red cell distribution width (%) (\leq 14, $>$ 14)
- Hepcidin (\leq Median, $>$ Median)
- hsCRP (\leq Median, $>$ Median)

Transferrin saturation is derived as S-Iron/TIBC * 100. See Section 4.2.17.2 for derivation of UACR.

Presentation

See presentation part of Section 4.2.1.4, however the p-value for each subgroup will be excluded. In addition, p-value of interaction will be presented for each subgroup. A forest plot will be

presented for difference in least squares means with 95% CIs. If any category of a subgroup variable contains less than 5% of the subjects in the full analysis set, separate ANCOVA models similar to the overall analysis will instead be fitted to subjects in each separate category, thus no p-value of interaction will be presented.

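### In the readable Part A SAP, the continuous effect modifiers other than age are tested for interaction only as two groups; a companion continuous term would recover power where the effect is smooth

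*SAP*

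**What the plan says.** SAP 4.2.1.7 lists the subgroup variables for the primary endpoints and states that a "p-value of interaction will be presented for each subgroup". Where a category holds less than 5% of the full analysis set, separate models are fitted and no interaction p-value is given.

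- **Median splits (seven):** NT-proBNP, S-cystatin C, MPO, UACR, ceruloplasmin, hepcidin and hsCRP. Typical entries are "MPO levels (\leq Median, $>$ Median" and "hsCRP (\leq Median, $>$ Median".
- **Fixed two-group cuts (eight):** BMI 30, KCCQ-TSS 80, 6MWD 350 m, LVEF 50%, neutrophils 4 × 10⁹/L, HbA1c 6.5%, eGFR 60 and red cell distribution width 14%. The walk-distance entry is "6MWD (meters) (\leq 350, >350".

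Sections 4.2.2.7, 4.2.5.6, 4.2.6.6 and 4.2.8.6 reuse this list for 6MWD, NT-proBNP, the echocardiographic parameters and the inflammatory biomarkers. The last three drop alcohol, nicotine, S-cystatin C and ceruloplasmin.

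The plan treats modification as continuous in two places, both for KCCQ-TSS:

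- In Part A, the fourth supplementary estimand (SAP 4.2, Table 2) reports the KCCQ-TSS effect as a function of baseline. SAP 4.2.2.6 gives the 6MWD counterpart a model with treatment, stratum and baseline only, and drops the figure.
- In Part B, the KCCQ-TSS model has a treatment-by-baseline product (Protocol 9.4.2.1), and Protocol 9.2 says: "For KCCQ-TSS, due to the assumed treatment-by-baseline interaction, the power was assessed through simulation".

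**The concern.** Cutting a continuous variable in two treats all subjects on one side of the cut as alike. If the treatment effect changes smoothly with the variable, the interaction test loses precision that the data already contain. A median cut also has no fixed value: it moves with the sample, so a finding above or below it is hard to carry into another study. A slope on the measured scale can be carried over.

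The programme has an interest in predictors of response. Protocol 8.6.4 collects samples to study "candidate biomarkers that show potential to predict response to treatment with AZD4831", and Part A informs further development. At stake is the sensitivity of an exploratory search for modifiers.

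**Working it through.** **1. The plan's own figures.** The documents give no power for the interaction tests. The nearest stated figure is Part A's main comparison (Protocol 9.2): 200 per arm, two-sided 0.05, 85% power for 6.0 KCCQ-TSS points, critical value 3.9.

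- SD 20 (SAP section 2): SE = 20 × √(2/200) = 2.0; power = Φ(6/2.0 − 1.96) = Φ(1.04) = 85%; critical value 1.96 × 2.0 = 3.92. This reproduces.
- SD 18 (Protocol 9.2): SE = 1.8 and power 91.5%. This does not reproduce, but SAP section 2 already corrects the SD to 20.
- 6MWD, SD 70 m: SE = 7.0; 21/7.0 = 3.0, so power is 85%; critical value 13.7 m. This reproduces.

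**2. Information kept by a cut.** Assume a normal modifier and a linear interaction. With a share p above the cut, the share of information kept is E = φ(z_p)² / [p(1 − p)], the squared correlation between the variable and its two-group version.

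- Median cut: 0.3989² / 0.25 = 0.637, a loss of 36%.
- 25/75 cut: 0.3178² / 0.1875 = 0.539, a loss of 46%.

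**3. Effect on power.** A continuous test with 80% power has noncentrality 1.960 + 0.842 = 2.802. The cut multiplies this by √E.

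- Median cut: 2.802 × 0.798 = 2.235; Φ(2.235 − 1.96) = 61%; 1/0.637 = 1.57 times the subjects for equal power.
- 25/75 cut: 2.802 × 0.734 = 2.056; Φ(2.056 − 1.96) = 54%; 1/0.539 = 1.86 times the subjects.

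**4. Simulation.** The interaction ANCOVA was simulated with 400 versus 200 subjects (pooled doses against placebo, about 600 evaluable), residual SD 20 and 4,000 runs.

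| Truth | Cut | Continuous term | Two groups |
|---|---|---|---|
| Linear | median | 81% | 61% |
| Linear | 25/75 | 77% | 53% |
| Step at the cut | median | 60% | 79% |
| Step at the cut | 25/75 | 53% | 80% |

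**5. How far the loss moves.** The documents give no distribution for any modifier. Shares come from the enrolment caps in Protocol 6.3 or are assumed.

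- KCCQ-TSS above 80, at most 30%: loss 42% at the cap.
- 6MWD at or above 350 m, at most 25%: loss 46% at the cap, and 51%, 57% or 66% if only 20%, 15% or 10% exceed the cut.
- Neutrophils above the cut, 60–80%: loss 38–51%.
- Uniform modifier, median cut: loss 25%.
- Log-normal biomarker, median cut: 36% if the effect is linear in the log; 48–82% if linear in the raw value (log SD 0.5–1.2, assumed).

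**6. The plan's own slope.** Protocol 9.2 assumes a change of 0.112 in treatment effect per KCCQ-TSS point. Noncentrality is d = 0.112 × SD_base × √(600 × 2/3 × 1/3) / SD_resid, with SD_base 15–22 assumed and SD_resid 18 or 20.

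- Low end: 0.112 × 15 × 11.55 / 20 = 0.97, power 16%.
- High end: 0.112 × 22 × 11.55 / 18 = 1.58, power 35%.
- With a 30/70 cut (multiply d by √0.576 = 0.759): 11% and 22%.

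**The case against.** The case for leaving the plan alone has real content.

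- **Several fixed cuts have a basis.** KCCQ-TSS 80 and 6MWD 350 m match the enrolment caps, neutrophils 4 is the randomisation stratum, and LVEF 50% is the boundary between heart-failure categories in Protocol 2.2. The complaint that a cut does not transfer applies only to the medians.
- **Linearity is also an assumption.** Replacing the two-group p-value would exchange one assumption for another and detach the p-value from the forest plot beside it. If the truth is a step at the cut, the linear term is the weaker test. This stands, and is why the continuous term should be added rather than substituted.
- **The text is incomplete.** The opening of 4.2.1.7, where the interaction model would be specified, cannot be read, and several exploratory sections are redacted. A continuous biomarker analysis could be there, so its absence from the plan cannot be asserted.

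A reader might also infer that the programme expects linear modification in general. It does not: linearity is assumed only for KCCQ-TSS in Part B, the Part B 6MWD model has no interaction term, and no section assumes a linear effect of MPO, NT-proBNP, hsCRP or UACR. Nor does Protocol 8.6.4 describe these tests; it concerns assay variability and bridging. What remains is that a continuous term uses data already collected and is more sensitive to a smooth effect.

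**Conclusion.** The point holds as an inexpensive improvement. In the readable text, the continuous modifiers other than age are tested for interaction only in two groups. For a roughly normal modifier with a linear effect, the cost is about 36% of the interaction information at a median split and 46% at a 25/75 split.

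Four stronger readings are not supported:

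- **That every continuous modifier is cut in two.** Age appears to have three groups (SAP 4.1.6.1; the list in 4.2.1.7 is truncated at that entry), and baseline KCCQ-TSS has a function-of-baseline analysis as well.
- **That 36–46% bounds the loss.** It is exact for two cases under stated assumptions. The 25% for 6MWD is a ceiling, so under the normal model the loss there is 46% or more; for other shapes it can be smaller or zero.
- **That true predictors are much more likely to be missed.** With the plan's own slope, a real interaction is missed 65–84% of the time on the full scale and 78–89% when cut. Power is low either way.
- **That the trial's conclusions are at risk.** The interaction tests lie outside the hierarchy in SAP 3.3.4, so the primary result and its type I error are unaffected.

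**What to change.** In SAP 4.2.1.7, prespecify for each continuous modifier a treatment-by-continuous-baseline interaction in the same ANCOVA, with the modifier's main effect in the model. Priority goes to the seven median-split biomarkers and baseline 6MWD. Use the log scale for NT-proBNP, MPO, hsCRP, UACR and hepcidin. Report the interaction slope, its 95% CI and p-value alongside the existing two-group estimates, interaction p-values and forest plot, and label them exploratory. The cross-referring sections then inherit the change.

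The cost is a short SAP addition and a few lines of code, with no new data. There are two downsides. The term targets a linear trend; the retained two-group estimates give only a rough check on that. It also adds up to fifteen exploratory p-values per primary endpoint, of which 15 × 0.05 = 0.75 would be expected below 0.05 if no modifier mattered.
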